3.0 Project Procedures

This will be a randomized pragmatic study for all patients ages 6-17 years with simple lacerations. Simple lacerations will be defined as lacerations within the scope of pediatric emergency medicine providers AND not requiring sedation or operative intervention. Subjects will be identified by the Emergency Department staff for enrollment. The goal number of enrolled participants will be 480, including 240 patients randomized into two groups, 120 per group, and 240 parents/guardians. The Emergency Department accepted to participate in this study and ED providers will complete the provider's survey. After signing the consent and assent form when appropriate, the patients will be randomized to either receive the standard of care or standard of care with immersive virtual reality goggles. Consent and assent will be obtained in the patient rooms within the emergency department. The standard of care shall be defined to include any of the following: local analgesia (topical LET and/ or subcutaneous lidocaine), oral or intranasal midazolam, distraction, Child Life Staff, or physical holding. Because each of the aforementioned interventions may vary between patients, it cannot be truly standardized; hence, this will be considered a pragmatic study. Patients randomized to the VR arm will receive the other standard procedures as well with VR goggles as an adjunct. Exclusion criteria include a history of epilepsy, visual or hearing impairment, or intellectual disability that would preclude use of VR goggles as determined by the guardian. Additionally, any lacerations around the eyes, eyebrows, and nose will be excluded as well as patients requiring sedation. Non-English speaking patients will be excluded as well. Hand lacerations will not be excluded.

Participants will be identified by ED staff following evaluation of the laceration. The ED staff will be given a flowchart with eligibility criteria. All interested participants who meet eligibility criteria will be consented. A research team member will obtain consent from parents or guardians by providing and reviewing the consent form (see Subject Consent Form). For patients who are between 8 and 17 years of age, a research team member will obtain assent by providing and reviewing the assent form (see Subject Assent Form). Consent and assent will be obtained in the patient's ED room.

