Patients will be separated into groups age 6-11 and 12-17. Patients will be randomized via a selection of a sealed envelope which will contain instructions for use of the VR goggles. The goggles utilized will be Lenovo Mirage Solo with DayDream, which are standalone VR headset with WorldSense Body Tracking. Research staff will coach the child on age-appropriate games, as previously determined by Lenovo.

The goggles will be cleansed with Oxivir Tb disinfectant wipes after each use and allowed to dry in room air prior to next use. Education will be provided to all ED providers on the proper cleansing protocol for the VR goggles (Figure 4). The disinfectant protocol will be available for all users during the study, and has been approved by the director of Infection Control at Children's Hospital of the King's Daughters.

Following the laceration repair, the patient, guardian and health care provider will be surveyed (Figure 1, 2, and 3) on paper surveys. The survey includes Likert-type scale questions, binary

questions as well as incorporates the Wong Baker Faces Pain Scale and Children's Fear Scale. The duration of the procedure will be recorded by the healthcare provider who completed the laceration repair. Time of procedure will be defined as from the time of irrigation to wound dressing. Patients and parents will both be filling out their own individual surveys. The parent should complete the survey first before the child should the child need assistance with completion. Patients and parents may decline to participate in any survey at any time.

The recruitment period will be from November 2021 until February 2021. Enrolled participants will not be compensated, and enrollment will be completely voluntary.

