4.0 Statistical Analysis

Continuous variables will be presented as mean, standard deviation, median, 25th, and 75th percentile. Categorical variables will be presented as frequency and percentage. Generalized Linear Model (GLM) will be used to assess the effect of intervention on the outcomes of the surveys. The correlation between provider's, parent's, patient's survey will be analyzed using the Spearman's correlation test. All statistical tests will be performed using the R software. All statistical tests will be 2-sided and $p < 0.05$ will be considered as statistically significant.

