5.0 Risks to Participants/ HIPAA Privacy Considerations

No personal identifiers will be recorded as part of the research study. Each enrolled participant will be given a unique number for data collection purposes. The risks involved in the study include adverse reactions to the VR goggles, which have been described to rarely cause nausea, vomiting, and motion sickness. There is a theoretical infection risk, but the VR goggles will be cleaned following a decontamination protocol following each use.

The data will be securely stored in RedCAP without any patient identifiers. The paper surveys will be kept in a locked drawer in a locked room within the Pediatric Department of Emergency Medicine offices.

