6.0 Budget

The Virtual Reality goggles are property of the Children's Hospital of the King's Daughters Child Life department. They will be stored in a locked drawer within the CHKD Emergency Department. This project is unfunded.

Figure 1. Use of Immersive Virtual Reality for Laceration Repairs in the Pediatric Emergency
Department
Patient Survey

1. How old are you? _____

2. Have you had stitches before? Yes
 No
 Unsure

3. Have you ever used Virtual Reality (VR) goggles before today? Yes
 No
 Unsure

4. Did you use VR goggles for your stitches today? Yes
 No

5. Would you use VR goggles again to get stitches? Yes
 No

6. During your stitches, did you have any of the following (select all that apply)?
 I did not experience any symptoms
 Dizziness
 Headache
 Nausea
 Vomiting
 Other (describe below)

7. How do you think the stitches went overall? Not well at all
 Somewhat not well
 Neutral
 Somewhat well
 Very well

8. The virtual reality goggles made the stitches seem less scary.
 Strongly disagree
 Disagree
 Neutral
 Agree
 Strongly agree

9. How would you rate your pain:

10. How would you rate how scared you were during the stitches:

[figure not shown]

Figure 2. Use of Immersive Virtual Reality for Laceration Repairs in the Pediatric Emergency
Department
Guardian Survey

1. **Patient Gender:**

Male
 Female
 Non-binary
 Self-identify
 Prefer not to say

2. What is the patient's age? _____

3. Please indicate if the patient has a developmental disability:

A. The patient does not have a developmental disability
B. Autism
C. Cerebral Palsy
D. Intellectual disability
E. Speech delay
F. _____

4. Has the patient had stitches previously? _____

Yes
 No
 Unsure

5. Has the patient ever used Virtual Reality (VR) goggles before today? _____

Yes
 No
 Unsure

6. Did the patient use VR goggles for the procedure today? _____

Yes
 No

7. If, yes, would you use VR goggles again for this procedure? _____

Yes
 No
 Did not use today

8. During the procedure did the patient experience any symptoms (select all that apply)?

Did not experience any symptoms
 Dizziness
 Headache
 Nausea
 Vomiting
 Other (*describe below*)

9. How do you think the procedure went overall?

- Not well at all
- Somewhat not well
- Neutral
- Somewhat well
- Very well

10. In your opinion, did the virtual reality goggles make the procedure seem less scary to the patient?

[figure not shown]
- Strongly disagree
- Disagree
- Neutral
- Agree
- Strongly agree

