11. How would you rate the patient's pain:

Wong-Baker FACES® Pain Rating Scale

12. How would you rate the patient's fear:

No fear A little fear Some fear A lot of fear The most fear

Figure 3. Use of Immersive Virtual Reality for Laceration Repairs in the Pediatric Emergency
Department
Provider Survey

1. Procedure Duration (*from irrigation to closure end*):
A. <10 minutes
B. 10-15 minutes
C. 16-20 minutes
D. 21-25 minutes
E. >25 minutes

2. Did the patient use VR goggles for the procedure today?
 Yes
 No

3. Would you recommend VR goggles again for this procedure?
 Yes
 No

4. Did the patient need to be held during the procedure?
 Yes
 No

5. Did the patient receive medicine intended to help them stay calm?
 Yes
 No

6. During the procedure, did the patient experience any symptoms (select all that apply)?
 Did not experience any symptoms
 Dizziness
 Headache
 Nausea
 Vomiting
 Other (*describe below*)

7. How do you think the procedure went overall?
 Not well at all
 Somewhat not well
 Neutral
 Somewhat well
 Very well

8. In your opinion, did the virtual reality goggles make the procedure seem less scary to the patient?

Strongly disagree
 Disagree
 Neutral
 Agree
 Strongly agree

9. How would you rate the patient's pain:

10. How would you rate the patient's fear:

[figure not shown]

Figure 4. Education Plan for Disinfection Protocol for Virtual Reality Goggles

1. The company insert for cleansing the virtual reality goggles will be printed, laminated, and physically located with the goggles in their carrying case.
2. The protocol for cleaning will be addressed during an Emergency Medicine division meeting prior to the start of the project and detailed in the meeting minutes.
3. The protocol will be addressed during a pediatrics monthly resident meeting and dispersed in an email from the chief residents.
4. The protocol will be emailed to all rotating residents prior to the start of their rotation.
5. The protocol will also be disseminated to nursing staff and ED techs via [name] prior to the start of the project.
6. Research project staff will be available either in person or by phone to answer any questions regarding the disinfection protocol during the study phase of the project. Contact information will be included inside the carrying case for the goggles as well as on all written communications (division meeting minutes, chief email, etc.)

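### The forms record goggles use but not the randomised arm, and section 4.0 does not say that the GLM groups patients as randomised

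*Combined protocol and SAP*

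**What the plan says.** **Allocation (section 3.0).** The design is a two-arm randomised comparison: "the patients will be randomized to either receive the standard of care or standard of care with immersive virtual reality goggles". The target is "240 patients randomized into two groups, 120 per group, and 240 parents/guardians". On the mechanism: "Patients will be randomized via a selection of a sealed envelope which will contain instructions for use of the VR goggles". Nothing further is said about how the result of the draw is written down.

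**Data capture (section 5.0 and Figures 1 to 3).** Section 5.0 says "Each enrolled participant will be given a unique number for data collection purposes" and that data are held in REDCap without identifiers. The patient form (Figure 1, item 4) asks "Did you use VR goggles for your stitches today". The guardian form (Figure 2, item 6) and the provider form (Figure 3, item 2) both ask "Did the patient use VR goggles for the procedure today". None of the three forms has an item for the assigned arm.

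**Analysis (section 4.0).** "Generalized Linear Model (GLM) will be used to assess the effect of intervention on the outcomes of the surveys". The section does not define the intervention variable or the analysis population. It does not say how a child who declines the goggles, or a control child who receives them, is to be classified.

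**The concern.** In most trial plans, a missing statement about analysis as randomised can be repaired at the analysis stage, because the allocation is in the data. Here that is not assured. Followed as written, the plan yields one treatment variable, namely whether goggles were used. If the arm is not noted when the envelope is opened, an analyst may have no means of restoring it. Section 5.0 keeps personal identifiers out of the research record, so no route back through the chart is described either.

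Departures from assignment are foreseeable from the protocol itself. The background describes children who physically resist repair, section 5.0 lists nausea, vomiting and motion sickness as risks of the headset, and all three forms ask about symptoms. A child who refuses the headset may do so for reasons related to pain or fear, which are the two primary outcomes. Under a grouping by use, that child's scores leave the VR group and join the controls. Use is also a softer variable than assignment: three respondents report it separately and may disagree, and a few minutes of wear can be called use or not.

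**Working it through.** **1. The plan's own figures.** 2 × 120 = 240 patients, and 240 + 240 parents/guardians = 480, as stated. The 120 per group cannot be reproduced, because no effect size, SD or power is given. For scale, at two-sided 0.05 the detectable difference with 120 per group and 80% power is (1.960 + 0.842) × √(2/120) = 0.36 SD.

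**2. When the two groupings differ.** If every child follows the assignment, use and arm are the same variable and the choice makes no difference. They separate only for children who depart from assignment.

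**3. Size of the difference.** From the documents: 120 per arm and two-sided 0.05. Assumed, because the documents are silent: no true effect of VR; a share d of the VR arm does not use goggles; no control child does; outcome SD 1; and non-use is the top d of a latent variable with correlation ρ to the outcome.

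- Group sizes by use: 120(1 − d) users and 120(1 + d) non-users.
- Non-users in the VR arm exceed users in that arm by g = ρλ/(1 − d). Here λ is the mean of a standard normal variable above its (1 − d) quantile.
- Bias of the comparison by use = 2dg/(1 + d) SD. The non-user group pools 120 controls, whose mean is dg above that of users, with 120d refusers, whose mean is g above it.
- SE = √(1/users + 1/non-users). The false-positive rate is P(|Z + bias/SE| > 1.96).

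With d = 10%: 108 users and 132 non-users, λ = 1.755, SE = √(1/108 + 1/132) = 0.130.

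- ρ = 0.5: g = 0.5 × 1.755/0.9 = 0.975. Bias = 2 × 0.1 × 0.975/1.1 = 0.18 SD. False-positive rate 28%.
- ρ = 0.3: g = 0.3 × 1.755/0.9 = 0.585. Bias = 2 × 0.1 × 0.585/1.1 = 0.11 SD. False-positive rate 13%.

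The same formulas over a range:

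| Non-use in VR arm (assumed) | Users vs non-users | ρ = 0.3: bias, false positives | ρ = 0.5: bias, false positives |
|---|---|---|---|
| 0% | 120 vs 120 | 0, 5% | 0, 5% |
| 5% | 114 vs 126 | 0.06 SD, 8% | 0.10 SD, 13% |
| 10% | 108 vs 132 | 0.11 SD, 13% | 0.18 SD, 28% |
| 20% | 96 vs 144 | 0.175 SD, 26% | 0.29 SD, 60% |

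A simulation of the same set-up (20,000 trials per scenario, t test by use) gave 13% and 27% at 10% non-use, in line with the formulas. With ρ = 0 the bias is zero at any level of non-use. With negative ρ it has the same size and the opposite sign.

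**4. The same trials compared as randomised.** The groups are 120 vs 120, the bias is zero and the false-positive rate is 5% under the null, whatever the level of non-use.

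**The case against.** The strongest reply is that the plan nowhere says the GLM groups patients by use. A reader might infer that it would compare self-selected users with non-users, but the documents do not support that. Section 3.0 defines the groups by randomisation, and in a randomised trial the effect of intervention can just as well mean the effect of the assigned arm. The one place where a group is defined by use is the usability scale in section 2.0, where restriction to users is appropriate. Use is also set mainly by the envelope, so self-selection applies only to children who depart from it.

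A second tempting inference is that the arm is held nowhere and that analysis as randomised is therefore impossible. That also goes too far. The documents include no data dictionary or enrolment log, and the three forms are evidently not the whole of data capture: the usability scale is planned but appears on none of them. An arm record tied to the study number is neither described nor excluded.

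A third is that any bias must favour VR. That holds only if the more distressed children decline. If calm children decline because they see no need for distraction, the sign reverses. A child who wears the goggles and then takes them off may still be marked as a user, so only outright refusers clearly change groups. A correlation of 0.5 is strong selection: at 10% non-use it puts refusers about 0.9 SD above average (0.5 × 1.755).

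These replies stand and make the point conditional. They do not remove it: no form holds the arm, no other record of it is described, and section 4.0 leaves the group variable open.

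**Conclusion.** The point holds as a gap in data capture and in the definition of the comparison, not as a demonstrated bias. Actual use is the only treatment variable the documents describe collecting, and nothing ties the GLM to the arm as randomised.

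The consequence depends on two things the documents do not settle: whether use would serve as the group variable, and how many children depart from assignment and why. Under the stated assumptions, 10% non-use would give a spurious difference of 0.11 to 0.18 SD, roughly a third to a half of the 0.36 SD detectable at 80% power. With full adherence there is no bias. The false-positive rates illustrate those assumptions; they are not properties of this plan.

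This is a cheap improvement. It is best made before recruitment, because an arm not recorded at the draw may not be recoverable.

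**What to change.** 1. When the envelope is opened, record the arm drawn against the study number, as one field on the provider form (Figure 3) and one in the REDCap record. No age-group box is needed, since age is already on the patient and guardian forms.
2. Add to section 4.0: *The primary GLM compares the arms as randomised, for all randomised patients with a score, regardless of goggles use.*
3. Keep the goggles-use items for describing adherence and for identifying who completes the usability scale.

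The cost is one tick box, one database field and one sentence. If an allocation log already exists, naming it in section 3.0 and adding the sentence in 4.0 is enough. The downside is slight dilution: if non-users gain nothing from VR, the as-randomised effect is (1 − d) times the effect in users, for example 0.9 times at an assumed 10% non-use. That is a natural quantity for a study the protocol calls pragmatic.

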1.0 Background and Rationale

Small procedures are an everyday occurrence in the pediatric emergency department. Medical procedures often elicit anxiety, which amplifies the pain response.ⁱ Laceration repair is one of the most common procedures performed. Simple laceration repair can be challenging not from a technical standpoint, but due to patient cooperation secondary to patient pain and anxiety.ⁱⁱ Usually, uncooperative children squirm, kick, twist, and scream; this is physically challenging during a laceration repair. It is the norm for patients to require distraction, analgesia, and anxiolytics as well as physical holding in order to achieve adequate patient stillness for safe repair. Typical passive distraction methods include watching television, playing on a tablet or phone, parental engagement, or Child Life involvement. Distraction is an accessible, low-cost, and non-pharmacologic intervention.

Virtual reality is an evolving technology that allows a viewer to be immersed into a simulated environment using a head mounted device as well as hand-held controllers. Immersive virtual reality is an active form of distraction. Children who actively perform tasks or engage in activities forget about their pain and fear.ⁱⁱⁱ Virtual reality has been documented in the literature as a safe and effective tool to reduce both pain and anxiety surrounding painful procedures in pediatrics as a distraction technique.^{iv} It has also been theorized to diminish pain signals during painful procedures.^v This technology has been studied in burn scrubs,^{vi} wound dressing changes,^{vii} immunizations,^{viii} venipuncture,^{ix} lumbar punctures,^x and dental procedures^{xi} in pediatrics. However, virtual reality (VR) has not been well described for laceration repair in the pediatric emergency department setting. Side effects might include nausea, vomiting, motion sickness, but these have not been proven to be significant outcomes in the literature.^{xii}

In our emergency department, the standard of care involves topical lidocaine/epinephrine/tetracaine (LET) cream and/or subcutaneous lidocaine, positioning, Child Life staff, and distraction. For some children, oral or intranasal anxiolysis is necessary as well as physical holding. Our aim for this study is to determine if Virtual Reality goggles can improve patient pain and anxiety scores during simple laceration repair when compared to standard passive distraction techniques.

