2.0 Objectives

The objective of this study is to determine if VR goggles can decrease patient pain and anxiety during simple laceration repairs. The primary outcome will be pain scores as assessed by the validated Wong Baker Faces Scale and anxiety scores as assessed by the validated Children's Fear Scale. A validated System Usability Scale (SUS) will be measured for each enrolled participant that used the VR goggles. Secondary outcomes include time of procedure, use of physical holding, adverse outcomes, and pharmacologic interventions.

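### The secondary outcome is use of physical holding, but its only field asks an unblinded provider whether the child needed holding, which is a judgement and not a record of what was done

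*Combined protocol and SAP*

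**What the plan says.** Section 2.0 (Objectives) states: "Secondary outcomes include time of procedure, use of physical holding, adverse outcomes, and pharmacologic interventions." The outcome is therefore whether holding was used.

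Section 3.0 (Project Procedures) lists the components of standard care, among them "oral or intranasal midazolam, distraction, Child Life Staff, or physical holding". The VR arm receives the other standard procedures with goggles added, so holding can occur in either arm.

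Section 3.0 also describes the data collection: "Following the laceration repair, the patient, guardian and health care provider will be surveyed (Figure 1, 2, and 3) on paper surveys." The Patient Survey (Figure 1) and Guardian Survey (Figure 2) contain no item on holding. The Provider Survey (Figure 3) has one, item 4, answered Yes or No: "Did the patient need to be held during the procedure?" The next item, on a comparable co-intervention, is worded as a fact: "Did the patient receive medicine intended to help them stay calm?" Two lines above item 4, the same provider answers "Did the patient use VR goggles for the procedure today?"

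Neither physical holding nor need is defined. No blinding, independent observer or chart abstraction is described.

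**The concern.** Use is an observable event. Need is an opinion about that event, given after the repair. The two can part in both directions: a child held as a precaution may be scored No, and a child who seemed to need holding but was not held may be scored Yes. The form has no other item from which actual holding could be recovered.

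The person answering knows whether goggles were worn, so the threshold for calling a hold needed could differ between arms. The primary outcomes, pain and fear ratings, are subjective by nature. Holding is one of the few outcomes in this open-label design that could be recorded as a plain fact, and the wording gives up some of that advantage. Section 4.0 applies a generalized linear model to the survey outcomes, so item 4 would enter the arm comparison as answered.

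**Working it through.** **The texts side by side.**

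| Place | What is asked or named | Type |
|---|---|---|
| Section 2.0 | use of holding | event |
| Provider Survey item 4 | need for holding | judgement |
| Provider Survey item 5 | receipt of calming medicine | event |

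Item 4 is the only one of the three worded as a judgement, and it is the only source for the outcome in the first row.

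**Figures in the plan.** Section 3.0 gives 120 per group, and 2 × 120 = 240 patients. Section 4.0 gives two-sided testing at 0.05. No holding rate, effect size or power is stated, so there is no plan figure for this outcome to reproduce. What follows is illustration.

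**Inputs.** From the documents: n = 120 per arm and two-sided alpha 0.05. Assumed: the true proportion held, p, is the same in both arms; a held child is reported as Yes with probability s_C in control and s_V in the VR arm; a child who was not held is never reported as Yes.

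**Formulas.** Recorded proportions are p₁ = p·s_C and p₂ = p·s_V, with difference d = p(s_C − s_V). With m = (p₁ + p₂)/2,

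- SE₀ = √[2m(1 − m)/n]
- SE₁ = √[p₁(1 − p₁)/n + p₂(1 − p₂)/n]
- P(significant, VR looks better) = Φ[(d − 1.96·SE₀)/SE₁]
- P(significant, VR looks worse) = Φ[(−d − 1.96·SE₀)/SE₁]

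Two-sided rejection is the sum of the last two.

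**One case in full.** With p = 30%, s_C = 90% and s_V = 70%: p₁ = 0.27, p₂ = 0.21, d = 0.06, m = 0.24. SE₀ = 0.0551 and SE₁ = 0.0550. Favouring VR: Φ[(0.06 − 0.1081)/0.0550] = 0.191. In the other direction: 0.001. Sum: 0.192.

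**Results.**

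| p | s_C vs s_V | Recorded | d (points) | Favouring VR (nominal 2.5%) | Two-sided (nominal 5%) |
|---|---|---|---|---|---|
| 30% | equal | equal | 0 | 2.5% | 5.0% |
| 30% | 95% vs 90% | 28.5% vs 27% | 1.5 | 4.4% | 5.8% |
| 30% | 95% vs 80% | 28.5% vs 24% | 4.5 | 12.1% | 12.4% |
| 30% | 90% vs 70% | 27% vs 21% | 6 | 19.1% | 19.2% |
| 40% | 95% vs 90% | 38% vs 36% | 2 | 5.1% | 6.2% |
| 40% | 95% vs 80% | 38% vs 32% | 6 | 16.2% | 16.3% |
| 40% | 90% vs 70% | 36% vs 28% | 8 | 26.3% | 26.4% |

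The table puts the lower reporting in the VR arm. That is a choice made for illustration: swapping s_C and s_V gives the same two-sided figures with the sign reversed.

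**Equal misreporting.** If s_C = s_V = s, a true difference D is recorded as s·D. For example, 30% vs 20% with s = 80% is recorded as 24% vs 16%, so 10 points become 8. No false difference arises, but a real one shrinks.

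**The case against.** The strongest reply is that need and use will often coincide here. Section 1.0 says it is the norm for patients to require several measures, "as well as physical holding in order to achieve adequate patient stillness for safe repair", and the same section speaks of holding as necessary for some children. Section 3.0 lists it among options that vary between patients. On that description holding is applied when required, and many providers will read item 4 as asking whether the child was held. This stands, and it limits the point: the documents do not show that children are held as routine without need.

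A reader might infer that under-reporting in the VR arm is the likely result and that the outcome is biased towards VR. The documents do not support that. Nothing in them shows how providers would read the word need by arm, and the opposite error (needed, not held, scored Yes) is equally open. A bias favouring VR is possible, no more.

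It is also fair to say that the larger rejection rates rest on assumed reporting gaps of 15 to 20 points. With a 5-point gap the two-sided rate is about 6%, close to nominal.

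These replies do not remove the mismatch. The stated outcome is an event, its only field asks for a judgement, and item 5 shows that the form can word a co-intervention as an event.

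**Conclusion.** The point holds in a limited form. Item 4 does not ask for the outcome that section 2.0 names, and the provider who answers it knows the arm. Where need and use diverge, the recorded outcome is wrong. The error may differ by arm, in a direction that cannot be settled from the documents, or be common to both arms and mainly dilute a difference.

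The size cannot be known from the plan. In the 30% illustration, two-sided rejection with no true difference runs from about 6% to 19% as the reporting gap grows from 5 to 20 points. This rests on the assumed holding rate, the assumed reporting probabilities and no false Yes answers.

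Severity is minor to moderate. One binary secondary outcome is affected; the primary pain and anxiety scores and the sample size are not.

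**What to change.** Reword Provider Survey item 4 as a factual question parallel to item 5, with a short definition built in. For example: *Was the patient physically held to keep them still (not comfort positioning or hand-holding) at any time during the procedure? Yes / No.* The exclusion in brackets matters, because a question about any holding by anyone would also count a parent holding a hand.

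Use the same procedure window as item 1. That window must first be reconciled: section 3.0 ends the procedure at wound dressing, while item 1 ends it at closure. If perceived need is also of interest, make it a separate item.

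The cost is one reworded line and an agreed definition. The same unblinded provider would still answer, so some rater bias remains; having someone else record the item would reduce dependence on the treating provider, where staffing allows. If forms are already in use, record the date of the change and do not pool answers to the two wordings without saying so.
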